### 4.3 Treatment Discontinuation

Patients who discontinue study medication early (for any reason) will remain in the study through the 52 week study period. Patients will have a 4 week follow-up visit after stopping study medication and then be followed up at a reduced visit schedule of every 8 weeks until the end of the study.

Patients will be discontinued from treatment for the following reasons (below and [Appendix H](#) and [Appendix O](#)):

- a. Disease progression: Diagnosis of AML during the study
- b. Liver Function: Discontinuation of treatment will occur if:
  - ALT or AST  $>8 \times$  ULN
  - ALT or AST  $>5 \times$  ULN for more than 2 weeks
  - ALT or AST  $>3 \times$  ULN and TBL  $>2 \times$  ULN or international normalized ration (INR)  $>1.5$  (If INR testing is applicable/evaluated)
  - ALT or AST  $>3 \times$  ULN with the appearance of fatigue, nausea, vomiting, right upper quadrant pain or tenderness, fever, rash and/or eosinophilia ( $>5\%$ )

A patient who decides to discontinue treatment with study medication will always be asked about the reason(s) for discontinuation and the presence of AEs (if any). These data will be ascertained and documented by the investigator and recorded in the electronic case report forms (eCRF) as appropriate. The patient should return all study medications.

Reasons for permanent discontinuation of treatment with study medication:

- Patient's decision (subject no longer wants to continue study medication (i.e., withdrawal of consent)
- Investigator's decision that it is in the best interest of the patient to be withdrawn from the study
- AEs (including SAEs)
- Significant noncompliance with study procedures, as determined by Investigator or Sponsor
- Lack of efficacy
- Treatment with ESAs
- Patient is lost to follow-up
- Site terminated by the Sponsor
- Pregnancy
- Death

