12.3.3.6. Mean Change from Baseline in Physical Functioning Subscale of PROMIS

The PROMIS PF item measures self-reported, current capability to carry out activities that require physical actions, ranging from self-care (activities of daily living) to more complex activities that require a combination of skills, often within a social context. The questionnaire will be administered at the Week 1 Day 1, Week 9, Week 17, Week 28 and Week 52 (or EOT). The PF 10-item short form which contains 10 questions will be used in this study, and each item is scored on a 5-point rating scale, with higher scores indicating better functioning. To find the total raw score, sum the values of the response to each question, with the lowest possible raw score is 10; the highest possible raw score is 50.

PROMIS items are not scored as sums, but rather on a standardized T-score metric ([Appendix 19.5](#)) using IRT. The standardized norm-based T-scores will be used in the summary. The mean change from Baseline in the PROMIS-SF v2.0 Physical Function 10b score will be summarized and analyzed. A mixed model for repeated measures (MMRM) with treatment, visit, treatment*visit, and stratification factors as fixed effects, the baseline score value and baseline*visit interaction as covariate will be used to assess treatment difference. The LSM and the corresponding 95% confidence intervals for the differences between roxadustat and the placebo group (roxadustat – placebo) will be presented along with the p-values for the treatment differences resulting from the model. The LSM for the difference will be considered clinically meaningful if it exceeds the distribution-based minimal clinically important difference (MCID) and will be marked in the results, see [Section 19.8.1](#) for details of MCID. An unstructured variance-covariance structure will be used to model the within-patient errors. This variance-covariance matrix will be estimated across treatment groups. If the model fails to converge, then the covariance structure that converges and with the highest REML log likelihood will be used.

Missing values will be handled by the MMRM model, utilizing data from all visits and all patients.

A sensitivity analysis will be conducted using Analysis of Covariance (ANCOVA) model with Last Observation Carries Forward (LOCF) imputation, see [Section 19.8.3](#) for details.

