Week 9 and week 52 are the analysis endpoint for 28-week and 52-week analysis respectively, the p-value obtained will be reported.

This analysis will take into account the potential intercurrent events as follows:

1. Treatment discontinuation due to reasons other than AE/SAE: using Treatment-policy strategy: regardless of these intercurrent events occurred;
2. Treatment discontinuation due to AE/SAE: using Hypothetical strategy: A scenario is envisaged in which the patient suffers from the worst quality of life after discontinuation treatment due to AE/SAE. If a patient discontinued treatment due to AE/SAE, all the missing PROMIS-SF v2.0 Physical Function 10b score afterward will be substituted with the worst possible scores before being used in descriptive summary and statistical models.
3. Death: using Treatment-policy strategy: regardless of these intercurrent events occurred. If a patient died, the PROMIS-SF v2.0 Physical Function 10b scores up to death will be used for analysis.

Line plot of mean and mean change from baseline over time with the associated standard error will be provided. A cumulative distribute plot will be presented to show the difference of patients achieving meaningful change in PROMIS-SF v2.0 Physical Function 10b score between two treatment groups.

A by-patient listing will also be provided.

The analysis will be conducted for FAS and PPS.

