1. Treatment discontinuation due to reasons other than AE/SAE: using Treatment-policy strategy: regardless of these intercurrent events occurred;

2. Treatment discontinuation due to AE/SAE: using Hypothetical strategy: A scenario is envisaged in which the patient suffers from the worst quality of life after discontinuation treatment due to AE/SAE. If a patient discontinued treatment due to AE/SAE, all the missing PROMIS-SF v1.0 Fatigue 13a score afterward will be substituted with the worst possible scores before being used in descriptive summary and statistical models.

3. Death: using Treatment-policy strategy: regardless of these intercurrent events occurred. If a patient died, the PROMIS-SF v1.0 Fatigue 13a scores up to death will be used for analysis.

Line plot of mean and mean change from baseline over time with the associated standard error will be provided. A cumulative distribute plot will be presented to show the difference of patients achieving meaningful change in PROMIS-SF v1.0 Fatigue 13a score between two treatment groups. A by-patient listing will also be provided.

The analysis will be conducted for FAS and PPS.

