1. Treatment discontinuation due to reasons other than AE/SAE: using Treatment-policy strategy: regardless of these intercurrent events occurred;
2. Treatment discontinuation due to AE/SAE: using Hypothetical strategy: A scenario is envisaged in which the patient suffers from the worst quality of life after discontinuation treatment due to AE/SAE. If

a patient discontinued treatment due to AE/SAE, all the missing EQ-5D-5L VAS scores afterward will be substituted with the worst possible scores before being used in descriptive summary and statistical models.

3. Death: using Treatment-policy strategy: regardless of these intercurrent events occurred. If a patient died, the EQ-5D-5L VAS scores up to death will be used for analysis.

Line plot of mean and mean change from baseline over time on EQ-5D assessment will be provided. A cumulative distribute plot will be presented to show the difference of patients achieving meaningful change in EQ-5D-5L VAS score between two treatment groups. A by-patient listing will also be provided.

The analysis will be conducted for FAS and PPS.

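### The HRQoL rules score a missing form after death more mildly than one after an adverse-event stop, and set no precedence for a fatal SAE

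*SAP*

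**What the plan says.** SAP 12.3.3.6, 12.3.3.7 and 12.3.3.8 each give three intercurrent-event rules, and Table 1 in SAP 4.2.2 repeats the strategies.

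- **Stop for AE/SAE (rule 2, labelled hypothetical).** For Physical Function, "all the missing PROMIS-SF v2.0 Physical Function 10b score afterward will be substituted with the worst possible scores". For fatigue, "all the missing PROMIS-SF v1.0 Fatigue 13a score afterward will be substituted with the worst possible scores". For the EQ-5D VAS, "all the missing EQ-5D-5L VAS scores afterward will be substituted with the worst possible scores".
- **Death (rule 3, labelled treatment policy).** For Physical Function, "If a patient died, the PROMIS-SF v2.0 Physical Function 10b scores up to death will be used for analysis". For fatigue, "If a patient died, the PROMIS-SF v1.0 Fatigue 13a scores up to death will be used for analysis". For the VAS, "If a patient died, the EQ-5D-5L VAS scores up to death will be used for analysis". Nothing is substituted after death.
- **Other missing scores.** "Missing values will be handled by the MMRM model, utilizing data from all visits and all patients". The fatigue and VAS sections say the same in substance. SAP 5.4 rules out any substitution that the SAP does not specify. The VAS section also limits its model to patients with a baseline and a post-baseline value at the visit concerned.

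Table 4 places these endpoints at Week 9, as Tests 8 to 10. The only missing-data sensitivity analysis is ANCOVA with LOCF (SAP 19.8.2). It runs after these rules and covers the two PROMIS scores but not the VAS.

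**The concern.** Rule 2 rests on the premise that a patient who stops for an AE then has the worst quality of life. Rule 3 gives a patient who dies a milder score, and no reason is offered for that order. The treatment-policy label cannot describe scores that do not exist after death.

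The HRQoL sections also depart from the rest of the SAP. Elsewhere, a death before Week 8 makes the patient a non-responder (12.3.1.1, 12.3.3.1, 12.3.3.2), and an AE/SAE stop and a death are written together as one cut-off (12.3.3.1 to 12.3.3.3, 12.3.3.5).

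A fatal SAE falls between the rules. Protocol 4.3 lists adverse events and death as separate reasons for stopping treatment, while Protocol 7.3.5.2 has every death reported as an SAE. Which rule applies could then depend on the reason recorded, and two programmers could code it differently. Three alpha-controlled tests and the Week 52 HRQoL analyses use these rules.

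**Working it through.** **Figures in the plan.** The SAP gives no power, SD, effect size or death rate for Tests 8 to 10, so there is no HRQoL design figure to reproduce. Its power statements concern the primary endpoint and do not bear on this point.

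**Inputs from the documents.**
- Arm sizes: 140 patients enrolled (SAP 17) at 3:2 gives 140 × 3/5 = 84 and 140 × 2/5 = 56. All 140 are taken to be in the analysis set.
- Worst Physical Function score: raw 10, T = 13.8 (SAP 19.5).
- Worst VAS: 0 (SAP 12.3.3.8).
- Worst fatigue: raw 65, T = 83.5 (SAP 19.6).

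**Assumed, not in the documents:** baseline means, SDs and event counts.

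**Shift per patient.** For a patient with no score in the window, and no mean change in the other patients, the arm mean moves by (worst score − baseline) / n if the patient is an AE stop. A death before any post-baseline score moves it by 0.

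| Endpoint | Assumed baseline | AE stop, n = 84 | AE stop, n = 56 | Death |
|---|---|---|---|---|
| Physical Function T | 35 / 40 / 45 | −0.25 / −0.31 / −0.37 | −0.38 / −0.47 / −0.56 | 0 |
| Fatigue T (higher is worse) | 50 / 55 / 60 | +0.40 / +0.34 / +0.28 | +0.60 / +0.51 / +0.42 | 0 |
| VAS | 50 / 60 / 70 | −0.60 / −0.71 / −0.83 | −0.89 / −1.07 / −1.25 | 0 |

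For example, (13.8 − 40)/84 = −0.31 and (0 − 60)/84 = −0.71. Shifts in the smaller arm are 84/56 = 1.5 times larger.

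**Who is affected at Week 9.** The scheduled day is 7 × (9 − 1) + 1 = 57. In SAP Table 7.7 the window runs from Day 1 post-dose to before Day 57 + 28 = 85. Protocol Appendix B schedules HRQoL at EOT for early stoppers. An AE stopper who completes that form before Day 85 therefore has an observed score, and rule 2 replaces only missing ones. Tests 8 to 10 are touched only by stops or deaths before about Day 85 with no form in the window.

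**Null simulation.** Physical Function at Week 9, 84 vs 56, ANCOVA on baseline, 4,000 runs per scenario, no true effect; assumed mean 40, SD 8, correlation 0.6.
- Four or eight roxadustat patients lack a score, none on placebo. As AE stops, the difference is −1.25 or −2.52 points, with a significant result against roxadustat in 10% or 34% of runs. As deaths, the difference is about 0, with about 2%.
- Equal event proportions, but deaths on roxadustat and AE stops on placebo (3 vs 2, 6 vs 4, 9 vs 6). The difference favours roxadustat by 0.9, 1.8 and 2.8 points, with significant superiority in 9%, 22% and 47% of runs against a nominal 2.5%.

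**Sensitivity analysis.** LOCF carries a deceased patient's last score forward, while an AE stopper keeps the worst score. The asymmetry survives.

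**Direction of fatigue.** SAP 12.3.3.7 says that higher scores mean better functioning. The items and table in SAP 19.6 run the other way: raw 13 is T = 30.3 (least fatigue) and raw 65 is T = 83.5 (most). If worst were coded from the text, an AE stop at baseline 55 would move the mean by (30.3 − 55)/84 = −0.29, an apparent improvement on the table's scale.

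**The case against.** Using scores only up to death is in substance a while-alive approach under the wrong label, and SAP 12.3.1.1 handles death on a comparable while-on-treatment basis. Giving death the worst score is one defensible estimand, not the only one. This stands as a general point. It does not explain why the same section gives a non-fatal AE stop the worst score and death a milder one, and it leaves the fatal SAE undefined.

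Four stronger readings are tempting, and the documents do not support them.

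- **A typical early AE stopper scores T = 13.8 at Week 9.** This requires the scheduled EOT form to be missed.
- **Tests 8 to 10 are biased towards the arm with more deaths in any absolute sense.** In the simulation, deaths alone moved the difference by about 0, with no excess of significant results. The advantage exists relative to scoring deaths like AE stops. The inflated superiority rates need deaths in one arm and AE stops with missing forms in the other, a pattern that no section predicts.
- **The effect nearly reaches the significance threshold.** Four to eight deaths at Week 52, with baseline 40, give 4 × 0.31 = 1.2 to 8 × 0.31 = 2.5 points. The threshold is 1.96 × 8 × √(1/84 + 1/56) = 2.7 for an assumed SD of change of 8. But Table 4 tests Week 9, and the added worst scores raise the variance. With 8 of 84 shifted by 26.2, the roxadustat variance is 64 + (8/84)(76/84)(26.2²) ≈ 123. Pooled with 64 on placebo, the SD is about 10 and the threshold about 3.4.
- **The AE/SAE rule plainly does not apply to a fatal SAE.** The SAP does not say so. A patient stopped for an SAE who later dies meets rule 2 as well as rule 3.

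**Conclusion.** The point holds for all three endpoints: death is scored more mildly than a non-fatal AE stop with a missing form, and a fatal SAE can score the worst value or nothing. Each affected patient in the 84-patient arm makes a difference of 0.25 to 0.37 Physical Function T-points (baseline 35 to 45 assumed) or about 0.7 VAS points (baseline 60 assumed), and 1.5 times that in the 56-patient arm.

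The effect on Tests 8 to 10 is probably small. Even with one to three such deaths by Week 9 (assumed), all in the larger arm, the Physical Function difference is 1 × 0.25 to 3 × 0.37, or about 0.3 to 1.1 points, and these tests are reached only if Tests 1 to 7 succeed. The Week 52 HRQoL analyses, outside the gatekeeping sequence, are more exposed because deaths accumulate. With no death rate or SD in the documents, the total cannot be fixed. The change should be made because the ranking is incoherent and the coding ambiguous, not because a result is shown to turn on it.

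**What to change.** In SAP 12.3.3.6 to 12.3.3.8 and Table 1:

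1. Score missing scheduled visits after death at least as badly as those after an AE/SAE stop, as a composite strategy.
2. State that a patient who stops for an AE/SAE and then dies, or who dies of an SAE, gets the same worst-score rule whichever reason is recorded.
3. Relabel as composite both the death rule (now treatment policy) and the worst-score substitution (now hypothetical).
4. Define the worst fatigue score as T = 83.5, in line with SAP 19.6, and correct the direction stated in 12.3.3.7.
5. Report the current scores-up-to-death model as a sensitivity analysis for all three endpoints, including the VAS.

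The cost is a few lines of text, one imputation flag and one extra set of model runs, with no new data. The downside is that a few extreme scores add variance, as the existing AE rule already does.

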12.3.3.7. Mean Change from Baseline in Fatigue Subscale of PROMIS

Fatigue will be measured in the study using the 13-item fatigue scale of the FACIT Measurement System, each item is scored on a 5-point rating scale ranging from 1 to 5 depicting “not at all” to “very much”, with higher scores indicating better functioning. The questionnaire is designed for self-completion by patients and will be administered at baseline, Week 9, Week 17, Week 28 and Week 52(or EOT).

PROMIS items are not scored as sums, but rather on a standardized T-score metric ([Appendix 19.6](#)) using IRT. The standardized norm-based T-scores will be used in the summary. The mean change from Baseline in the PROMIS-SF v1.0 Fatigue 13a score over time will be summarized and analyzed using the FAS and PPS Population. The analysis window is defined in [Appendix 19.3.1](#).

A mixed model for repeated measures (MMRM) with treatment, visit, treatment*visit, and stratification factors as fixed effects, the baseline score value and baseline*visit interaction as covariate will be used to assess treatment difference. The LSM and the corresponding 95% confidence intervals for the differences between roxadustat and the placebo group (roxadustat – placebo) will be presented along with the p-values for the treatment differences resulting from the model. The LSM for the difference will be considered clinically meaningful if it exceeds the distribution-based minimal clinically important difference (MCID) and will be marked in the results, see [Section 19.8.1](#) for details of MCID. An unstructured variance-covariance structure will be used to model the within-patient errors. This variance-covariance matrix will be estimated across treatment groups. If the model fails to converge, then the covariance structure that converges and with the highest REML log likelihood will be used.

Missing value will be handled by the MMRM model, utilizing data from all visits and all patients.

A sensitivity analysis will be conducted using Analysis of Covariance (ANCOVA) model with Last Observation Carries Forward (LOCF) imputation, see [Section 19.8.2](#) for details.

Week 9 and week 52 are the analysis endpoint for 28-week and 52-week analysis respectively, the p-value obtained will be reported.

This analysis will take into account the potential intercurrent events as follows:

1. Treatment discontinuation due to reasons other than AE/SAE: using Treatment-policy strategy: regardless of these intercurrent events occurred;

2. Treatment discontinuation due to AE/SAE: using Hypothetical strategy: A scenario is envisaged in which the patient suffers from the worst quality of life after discontinuation treatment due to AE/SAE. If a patient discontinued treatment due to AE/SAE, all the missing PROMIS-SF v1.0 Fatigue 13a score afterward will be substituted with the worst possible scores before being used in descriptive summary and statistical models.

3. Death: using Treatment-policy strategy: regardless of these intercurrent events occurred. If a patient died, the PROMIS-SF v1.0 Fatigue 13a scores up to death will be used for analysis.

Line plot of mean and mean change from baseline over time with the associated standard error will be provided. A cumulative distribute plot will be presented to show the difference of patients achieving meaningful change in PROMIS-SF v1.0 Fatigue 13a score between two treatment groups. A by-patient listing will also be provided.

The analysis will be conducted for FAS and PPS.

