12.3.2. Sequential Gatekeeping Procedure

Once the primary hypothesis has been rejected for the primary endpoint, the primary endpoint at week 52 and the secondary endpoints in the order specified in the Table 4 will be tested using a sequential gatekeeping procedure, in order to maintain the overall two-sided type I error of 0.05. If p-value from a test is < 0.05 , the claim of superiority will be considered successful, and the test will progress to the next comparison in sequence as follows.

Table 4: Sequential Gatekeeping Procedure

Test	Variable	Comparison
1	Proportion of patients who achieved TI ≥ 56 consecutive days (e.g., 8 weeks) since first dose in the first 28-weeks of treatment	Superiority of roxadustat versus placebo
2	Proportion of patients who achieved TI ≥ 56 consecutive days (e.g., 8 weeks) since first dose in the 52-weeks of treatment	Superiority of roxadustat versus placebo
3	Proportion of patients who achieved TI ≥ 56 consecutive days (e.g., 8 weeks) anytime during the study	Superiority of roxadustat versus placebo
4	Proportion of patients who achieved $\geq 50\%$ reduction in number of pRBC transfusions over 8 weeks compared to their Baseline for any 8-week period during the study	Superiority of roxadustat versus placebo
5	Cumulative number of patient-exposure-weeks (PEW) of TI over the first 28 weeks of the treatment period	Superiority of roxadustat versus placebo
6	Number of pRBC transfused change from baseline over the first 28 weeks of the treatment period	Superiority of roxadustat versus placebo
7	Proportion of patients who achieved TI for ≥ 20 consecutive weeks (140 consecutive Days)	Superiority of roxadustat versus placebo

8	Mean change from baseline in the PROMIS-SF v2.0 Physical Function 10b score at week 9	Superiority of roxadustat versus placebo
9	Mean change from baseline in the PROMIS-SF v1.0 Fatigue 13a score at week 9	Superiority of roxadustat versus placebo
10	Mean change from baseline in EQ-5D-5L VAS score at week 9	Superiority of roxadustat versus placebo

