19.6. Fatigue – Short Form 13a

Please respond to each question or statement by marking one box per row.

During the past 7 days...		Not at all	A little bit	Somewhat	Quite a bit	Very much
HI7	I feel fatigued	 1	 2	 3	 4	 5
HI12	I feel weak all over	 1	 2	 3	 4	 5
AN1	I feel listless ("washed out").....	 1	 2	 3	 4	 5
AN2	I feel tired	 1	 2	 3	 4	 5
AN3	I have trouble starting things because I am tired.....	 1	 2	 3	 4	 5
AN4	I have trouble finishing things because I am tired.....	 1	 2	 3	 4	 5
AN5	I have energy	 5	 4	 3	 2	 1
AN7	I am able to do my usual activities	 5	 4	 3	 2	 1
AN8	I need to sleep during the day.....	 1	 2	 3	 4	 5
AN12	I am too tired to eat	 1	 2	 3	 4	 5
AN14	I need help doing my usual activities	 1	 2	 3	 4	 5
AN15	I am frustrated by being too tired to do the things I want to do.....	 1	 2	 3	 4	 5
AN16	I have to limit my social activity because I am tired.....	 1	 2	 3	 4	 5

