Instructions: You can use the following conversion table to translate the total raw score into a T-score for each participant. These conversions are accurate ONLY when all questions on the short form have been answered.

PROMIS-SF v1.0 Fatigue 13a Scoring Table

Fatigue 13a (FACIT-Fatigue) - Adult v1.0					
Short Form Conversion Table					
Raw Score	T-score	SE*	Raw Score	T-score	SE*
13	30.3	4.7	40	60.8	1.8
14	35.0	3.5	41	61.4	1.8
15	38.0	3.0	42	62.0	1.8
16	40.3	2.8	43	62.6	1.8
17	42.1	2.6	44	63.2	1.8
18	43.7	2.5	45	63.8	1.8
19	45.0	2.3	46	64.4	1.8
20	46.3	2.2	47	65.0	1.8
21	47.3	2.1	48	65.6	1.8
22	48.3	2.0	49	66.2	1.9
23	49.3	2.0	50	66.9	1.9
24	50.1	1.9	51	67.5	1.9
25	51.0	1.9	52	68.2	1.9
26	51.7	1.9	53	68.9	2.0
27	52.5	1.9	54	69.6	2.0
28	53.2	1.9	55	70.4	2.0
29	53.9	1.8	56	71.2	2.1
30	54.6	1.8	57	72.0	2.2
31	55.3	1.8	58	72.9	2.3
32	55.9	1.8	59	73.9	2.4
33	56.6	1.8	60	75.0	2.5
34	57.2	1.8	61	76.2	2.7
35	57.8	1.8	62	77.5	2.9
36	58.4	1.8	63	79.1	3.1
37	59.0	1.8	64	81.2	3.3
38	59.6	1.8	65	83.5	3.4
39	60.2	1.8			

*SE = Standard Error on T-score metric

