19.8.2. Sensitivity Analysis of PROMIS

Sensitivity analysis will be conducted using Analysis of Covariance (ANCOVA) model for PROMIS Physical Function T-scores and Fatigue T-scores using Last Observation Carries Forward (LOCF) imputation for the FAS and the PPS, respectively. The LOCF imputation should be performed after any data handling for the intercurrent events as described in [Section 12.3.3.6](#) and [Section 12.3.3.7](#).

An ANCOVA model with treatment and stratification factors as fixed effects, the baseline score value as covariate will be used to assess treatment difference. The LSM and the corresponding 95% confidence intervals for the differences between roxadustat and the placebo group (roxadustat – placebo) will be presented along with the p-values for the treatment differences resulting from the model. The LSM for the difference will be considered clinically meaningful if it exceeds the MCID and will be marked in the results, see [Section 19.8.1](#) for details of MCID.

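### SAP 12.3.3.7 states the PROMIS Fatigue scale the wrong way round, so the worst-score imputation value and the favourable sign of Test 9 are not fixed

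*SAP*

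**What the plan says.** SAP 12.3.3.7 analyses Fatigue as norm-based T-scores taken from SAP 19.6. It gives one statement of direction, that items are scored 1 to 5, "with higher scores indicating better functioning. The questionnaire is designed for self-completion by patients". For patients who stop treatment because of an AE/SAE it says "all the missing PROMIS-SF v1.0 Fatigue 13a score afterward will be substituted with the worst possible scores", with no number attached. Table 1 in SAP 4.2.2 gives none either.

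SAP 19.6 prints the form, whose first item is "I feel fatigued", coded 1 for the lowest answer and 5 for the highest. It also prints the table headed "Fatigue 13a (FACIT-Fatigue) - Adult v1.0", which converts raw 13 to T 30.3 and raw 65 to T 83.5.

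Test 9 of the gatekeeping sequence (SAP 12.3.2, Table 4) is "Mean change from baseline in the PROMIS-SF v1.0 Fatigue 13a score at week 9", listed as superiority of roxadustat. Success is declared on p < 0.05, and SAP 12.1 makes all tests two-sided. The contrast is roxadustat minus placebo.

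SAP 12.3.3.7 and 19.8.2 share an MCID rule, which 19.8.2 words as "The LSM for the difference will be considered clinically meaningful if it exceeds the MCID and will be marked in the results". For the sensitivity analysis, 19.8.2 adds "The LOCF imputation should be performed after any data handling for the intercurrent events".

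**The concern.** The only sentence that states the direction of the scale contradicts the instrument it describes. Three rules depend on that direction.

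- **Imputation.** Anyone programming from the sentence would insert the lowest T-score, which on this form is a patient with no fatigue at all. Patients who stopped for an adverse event would then receive the best attainable score.
- **Superiority in Test 9.** The success rule looks only at the p-value, and no favourable sign is stated. If the sentence is followed throughout, a true reduction in fatigue is read as harm, and an increase as superiority. Test 10 is reached only through Test 9.
- **The clinical-relevance mark.** The MCID is a positive quantity (half an SD, or one SEM, in SAP 19.8.1). Read literally on roxadustat minus placebo, a benefit on Fatigue is negative and can never exceed it, while a harm can. Correcting the direction sentence alone would not cure this. The plot of patients with a meaningful change also needs a direction.

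If 19.6 is followed for every step, nothing is reversed. The problem is that the SAP does not say which of its two directions governs.

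**Working it through.** **Direction from the form (SAP 19.6).** Eleven of the 13 items are symptom statements coded 1 (not at all) to 5 (very much). The two positively worded items, AN5 (energy) and AN7 (usual activities), are printed with codes 5 down to 1. A higher code therefore means more fatigue on every item.

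- Least fatigued respondent: 13 × 1 = 13, T = 30.3
- Most fatigued respondent: 13 × 5 = 65, T = 83.5

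These reproduce the ends of the printed table. All 53 rows were checked, and T rises at every step. The scale therefore runs towards worse fatigue.

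**Does anything else settle it?** SAP 5.5 says a negative change is a decrease but not whether a decrease is good. SAP 12.3.3.6 uses the same higher-is-better clause for Physical Function, where it agrees with that form. SAP 12.3.3.8 anchors the EQ-5D VAS at 0 worst and 100 best. Of the three gatekept quality-of-life scales, only Fatigue contradicts its own scoring.

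**Gap per imputed value.** 83.5 − 30.3 = 53.2 T-points.

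**Effect on the treatment difference.** SAP 17 reports 140 patients enrolled and SAP 3.3 allocates 3:2. An exact split is assumed: 140 × 3/5 = 84 roxadustat and 140 × 2/5 = 56 placebo. Let kR and kP be the patients imputed at a visit. Using 30.3 instead of 83.5 changes roxadustat minus placebo by

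−53.2 × (kR/84 − kP/56).

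The documents give no counts, so these are illustrations:

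| Imputed (roxadustat vs placebo) | 53.2 × kR/84 | 53.2 × kP/56 | Change in difference |
|---|---|---|---|
| 3 vs 2 | 1.90 | 1.90 | 0.00 |
| 5 vs 1 | 3.17 | 0.95 | −2.22 |
| 8 vs 2 | 5.07 | 1.90 | −3.17 |
| 1 vs 3 | 0.63 | 2.85 | +2.22 |

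A lower difference is the beneficial direction on this scale. The wrong value therefore flatters whichever arm has proportionately more imputed patients.

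For scale, assume a T-score SD of 10 (range 8 to 12; the documents give none). A simple two-sample SE is 10 × √(1/84 + 1/56) = 1.73. The 8 vs 2 change is then 3.17/1.73 = 1.8 SE (1.5 SE at SD 12, 2.3 SE at SD 8).

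**Where it lands.** SAP Table 7.7 schedules Week 9 at Day 7 × (9 − 1) + 1 = 57, with a window from Day 1 post-dose to before Day 57 + 28 = 85. Protocol Appendix B collects the questionnaires at EOT. A patient who stops before Day 85 will therefore usually have an observed score in the Week 9 window.

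A simulated repeated-measures model shows the consequence (20 runs, 140 patients, four visits, unstructured covariance; assumed baseline mean 56, baseline SD 9, residual SD 7, correlation 0.6). Absolute change in the difference between the two imputed values:

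| Scenario | Week 9 | Weeks 17, 28, 52 |
|---|---|---|
| 5 vs 1, only later visits imputed | 0.02 | 2.20 each |
| 8 vs 2, only later visits imputed | 0.01 | 3.16 each |
| 5 vs 1, all visits imputed | 2.23 | 2.23 each |
| 8 vs 2, all visits imputed | 3.16 | 3.16 each |

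**The case against.** The best defence is that a careful programmer would get this right. SAP 12.3.3.7 describes the imputation scenario as a patient with the worst quality of life, refers to 19.6 for scoring and anchors the items from not at all to very much. Imputing 30.3 would mean treating an unfatigued patient as the worst case. That makes the error less likely, but the programmer would have to disregard the SAP's only statement of direction.

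Several gaps are not peculiar to Fatigue. Physical Function and the VAS also lack a numbered worst score, and Table 4 prints no favourable sign for any test, including Test 6, where fewer transfusions is the benefit. This is true. For those two scales, however, the stated direction agrees with the scoring, so the worst scores follow without ambiguity (T 13.8 and 0). With no imputed values, the two-sided p-value for Fatigue does not depend on the label.

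The MCID is naturally read as a size, and the mark it controls gates no test. That is fair, and it keeps this part minor, but the literal rule still marks only harm on this scale.

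The strongest limit is on size. Table 4 tests Fatigue only at Week 9, Test 9 is reached only if Tests 1 to 8 succeed, and Week 9 imputation should be rare. The larger shifts fall outside the gatekeeping sequence, assume the imputed patients are missing from Week 17 onward, and use illustrative counts. All of this stands.

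**Conclusion.** The concern holds. Section 12.3.3.7 is wrong as written, and the error sits in an analysis rule for a gatekept secondary endpoint. The gap of 53.2 T-points per imputed value comes directly from the SAP's own table.

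The effect on the results is conditional. It is zero if imputation is proportionate between arms, and about 2 to 3 T-points at an affected visit for the unbalanced counts shown. For Test 9 at Week 9 it is probably close to zero, unless Week 9 scores themselves are missing. The imputation effect falls mainly on later visits, the Week 52 analysis and the LOCF sensitivity analysis, which is run after the substitution. These sizes rest on the assumed 84:56 split, the illustrative counts and the simulation settings.

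The sign of superiority and the MCID mark are affected however many values are imputed. The primary analysis is not affected. This should be corrected before unblinding, so that neither the imputed value nor the winning direction can be chosen with results in view.

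**What to change.** In SAP 12.3.3.7, replace the direction clause with: *higher raw and T-scores indicate worse fatigue*. Then add:

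- the worst possible score is raw 65 (T = 83.5);
- benefit is a negative roxadustat-minus-placebo difference;
- superiority in Test 9 requires two-sided p < 0.05 with a negative difference;
- the difference is marked as a clinically meaningful benefit when it is below −MCID.

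Apply the same sign rule to Fatigue in SAP 19.8.2, and use the same direction for the meaningful-change plot. The cost is SAP wording only, with no new data and no change to the model.
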